7.3 Duration of Participation

Describe how long subjects will be involved in this research study. Include the number of sessions and the duration of each session - consider the total number of minutes, hours, days, months, years, etc.

12 Weeks.

7.4 Test Article(s) (Study Drug(s) and/or Study Device(s))

7.4.1 Description

Provide a brief description of all test articles (drugs (including any foods and dietary supplements), devices and/or biologics used in the research including the purpose of their use

and their approval status with the Food and Drug Administration (FDA). Include information about the form of the drug product (e.g., tablets, capsules, liquid).

Medical Device to be used in the Proposed

Study (Provided by Manufacturer): The InTENSity Select Combo II stimulator is a portable electrotherapy device featuring four therapeutic modes: Transcutaneous Electrical Nerve Stimulator (TENS), Neuromuscular Electrical Stimulation (NMES), Interferential (IF) and Russian which are used for pain relief. The stimulator sends gentle electrical current to underlying nerves and muscle group via electrodes applied on the skin. The parameters of device are controlled by the buttons on the front panel. The intensity level is adjustable according to the needs of patients.

Approval status with the Food and Drug Administration (FDA): 510(k) approved

Indications for NMES (provided by manufacturer)

Select Combo II Stimulator may be used for the following conditions:

- 1) Symptomatic relief of chronic intractable pain.
- 2) Post traumatic pain.
- 3) Post surgical pain.
- 4) Relaxation of muscle spasm.
- 5) Increase of blood flow circulation.
- 6) Prevention of disuse atrophy.
- 7) Muscle re-education.
- 8) Maintaining or increasing range of motion.
- 9) Immediate post-surgical stimulation of lower leg muscles to prevent venous thrombosis.

Proposed use of the device

This device will be used within the indications provided by the manufacturer. Specifically, 'prevention or retardation of disuse atrophy' of calf muscles after Achilles tendon repair surgery. However, although this device is intended to prevent atrophy, NMES has not been applied as part of the rehabilitation strategy for patients undergoing Achilles tendon repair surgery. Therefore, this study plans to evaluate the effect of applying NMES to calf muscles on functional outcomes used to evaluate recovery from Achilles tendon rupture. In the NMES will be applied in addition to standard therapy.

7.4.2 Treatment Regimen

Describe dose, route of administration and treatment duration. Include information about dose adjustments.

The stimulation group will follow the NMES protocol proposed in table 2 and Figure 2. The intensity will range between 15 and 30 mA.

7.4.3 Method for Assigning Subject to Treatment Groups

Describe the randomization process and how the associated treatment assignment will be made.

A master list with patient codes will be prepopulated with randomly assigned treatments. As recruitment is performed, patients will be assigned a code with the corresponding intervention. The randomization will be performed at a 1:1 ratio between control and stimulation group.

7.4.4 Subject Compliance Monitoring

Insert the procedures for monitoring subject compliance.

The stimulation device provides an activity log that will be used to monitor compliance. Additionally, entries to the pain and activity diary will be also used to evaluate compliance.

7.4.5 Blinding of the Test Article

Describe how the test article is blinded.

N/A

7.4.6 Receiving, Storage, Dispensing and Return

7.4.6.1 Receipt of Test Article

Describe how the test article will be obtained and from what source. Describe how the study test article will be packaged along with amounts (e.g., number of tablets/capsules or volume of liquid) and labeling. If drug kits are used, describe all the contents of the kit and associated labeling.

The device will be purchased from manufacturer. The device in case that includes cables, pads, batteries and a user manual.

7.4.6.2 Storage

Describe the plans to store, handle the test article so they will be used only on subjects and only by authorized investigators. Describe storage temperature requirements and how temperature will be monitored and recorded.

Device cases will be labeled with "Do not use if you are not part of the Neuromuscular Electrical Stimulation for Achilles Tendon Rupture Rehabilitation Study"

7.4.6.3 Preparation and Dispensing

Describe how the test article will be assigned to each subject and dispensed. Describe the steps necessary to prepare the test article. Include where the test article preparation will be done and by whom. Fully describe how the study treatment is to be administered and by whom.

The research team or clinician of the research team will demonstrate the NMES procedure to the participants. The research team will verify that the procedure is applied properly and corrects any problems with the protocol.

7.4.6.4

Return or Destruction of the Test Article

Describe the procedures for final reconciliation of the test article supply at the end of the study and whether the test article is to be shipped back to a source or destroyed on site.

At the week-6 visit, patients will return the stimulation device to a member of the study team.

7.4.6.5

Prior and Concomitant Therapy

Describe what prior and/or concomitant medical therapy will be collected. Describe which concomitant medicines/therapies are permitted during the study. Describe which concomitant medicines are not permitted during the study.

Patients can follow standard rehabilitation while using the stimulation device.

8.0 Subject Numbers and Statistical Plan

8.1 Number of Subjects

Indicate the maximum number of subjects to be accrued/enrolled. Distinguish between the number of subjects who are expected to be enrolled and screened, and the number of subjects needed to complete the research procedures if applicable (i.e., numbers of subjects excluding screen failures.)

50 Participants will be enrolled.

8.2 Sample size determination

If applicable, provide a justification of the sample size outlined in section 8.1 to include reflections on, or calculations of, the power of the study.

Two independent sample proportion comparison test was to compute the sample size using G* Power 3.1. A power analysis was performed based on the proportion of participants able to perform a heel rise at week 12, which is a strong predictor of long-term outcomes. With current rehabilitation strategies, 50% of participants are able to perform a single heel-rise at week 12. A clinically-significant improvement that would justify the application of the proposed treatment would be that 85% of participants would perform a heel-rise. A minimum of 22 subjects should be recruited in each group to achieve 80% power, with 5% significant level, equal allocation, to detect a significant difference between the two groups. Assuming an attrition rate similar to our previous studies of 10%, the total number of subjects in the NMES group should be 25.

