3.3.2 Follow-up for withdrawn subjects

Describe when and how to withdraw subjects from the study; the type and timing of the data to be collected for withdrawal of subjects; whether and how subjects are to be replaced; the follow-up for subjects withdrawn from investigational treatment.

Data collected up to the time of withdrawal may be used in the study. Subjects will be recruited until the desired number of participants with complete data points is reached. Subjects who experience AEs that are potentially related to the intervention will be followed via phone call or email to obtain information on how the AE resolves.

Participants who experience any of the above mentioned AEs will be followed up until resolved or stabilized.

Subject will be asked for consent to be contacted for possible future studies. Withdrawn subjects will be contacted if new information is available concerning the methods and techniques used in the study.

The subjects who withdraw from the study will not be replaced.

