8.3 Statistical methods

Describe the statistical methods (or non-statistical methods of analysis) that will be employed.

We will recruit 25 participants to participate in the NMES intervention and 25 for standard rehabilitation (control). Summary statistics for variables of interest including recruitment, retention, adherence, and reported pain will be calculated. To test the difference between groups (NMES and control), we will quantify the odds ratio and the 95% confidence interval of performing a single heel-rise test. If the bottom end of the confidence interval is higher than 1.0, the improvement will be significant. Chi-square goodness of fit will be used to study the associations between groups and covariates such as gender, activity, and age. Cochran-Mantel-Haenszel test will be used to evaluate the consistency of such associations.

Protocol deviations, such as missing visits, or lost to follow up (within the 10% already considered in the power analysis) will have a negligible effect on the statistical analysis since the proposed analysis can have unbalanced groups. The planned interim safety analyses will quantify the odds ratio between adverse events in the intervention group and standard of care. If the bottom end of the confidence interval is higher than 1.0, the incidence of AEs in the intervention group will be significant higher than that of standard care.

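### The 80% power claimed in 8.2 for 22 per group fits a one-sided 5% test; under the 95% interval rule in 8.3 power is about 69–71%, and about 77% with 25 per group

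*Combined protocol and SAP*

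**What the plan says.** Section 8.2 rests the sample size on two rates for the primary endpoint. For control, "With current rehabilitation strategies, 50% of participants are able to perform a single heel-rise at week 12"; the improvement that would justify the treatment "would be that 85% of participants would perform a heel-rise". It concludes that "A minimum of 22 subjects should be recruited in each group to achieve 80% power, with 5% significant level, equal allocation". With 10% attrition, "the total number of subjects in the NMES group should be 25", and 8.3 sets 25 for control as well. Sidedness is not stated.

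Section 8.3 gives the primary analysis: "we will quantify the odds ratio and the 95% confidence interval of performing a single heel-rise test". The decision rule follows: "If the bottom end of the confidence interval is higher than 1.0, the improvement will be significant". Neither section mentions a one-sided bound or a 90% interval, and neither says how the interval will be computed.

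On how many participants will be evaluable, section 3.3.2 says both that "Subjects will be recruited until the desired number of participants with complete data points is reached" and that "The subjects who withdraw from the study will not be replaced".

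**The concern.** The power calculation and the decision rule appear to use different error rates. Requiring the lower end of an ordinary 95% interval to exceed 1.0 allows a false positive in the favourable direction about 2.5% of the time. A sample size calculated at one-sided 5% is too small for that rule.

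This is the only power statement for the primary endpoint. If it belongs to a test the plan will not run, readers and oversight bodies are told that the chance of missing the target effect is 20% when it is higher. A non-significant result would then be read as stronger evidence against the intervention than it is.

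**Working it through.** **Inputs.** From 8.2: p0 = 0.50, p1 = 0.85, 1:1 allocation, 5% level, 80% power, 22 per group, 10% attrition. From 8.3: 25 per group, and success if the lower 95% limit of the odds ratio exceeds 1. The difference is d = 0.35 and the target odds ratio is (0.85/0.15)/(0.50/0.50) = 5.67.

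**Step 1: reproduce 22.** The pooled two-proportion formula is

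n = [z_α √(2 p̄ q̄) + z_β √(p0q0 + p1q1)]² / d²

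with p̄ = 0.675, √(2 × 0.675 × 0.325) = 0.6624, √(0.25 + 0.1275) = 0.6144 and z_β = 0.8416.

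- One-sided 5% (z = 1.645): (1.0895 + 0.5171)² / 0.1225 = 21.07, so 22. This matches the plan.
- Two-sided 5% (z = 1.960): (1.2982 + 0.5171)² / 0.1225 = 26.90, so 27.

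The attrition step also reproduces: 22/0.9 = 24.4, so 25.

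Other standard formulas, n per group for 80% power:

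| Formula | One-sided 5% | Two-sided 5% |
|---|---|---|
| Pooled | 22 | 27 |
| Unpooled | 20 | 25 |
| Arcsine | 21 | 27 |
| Continuity-corrected | 27 | 33 |

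Only the one-sided pooled formula gives 22, and no two-sided variant gives fewer than 25.

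**Step 2: power at two-sided 5% by the same formula.** Power = Φ{[d√n − z_α √(2 p̄ q̄)] / √(p0q0 + p1q1)}.

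- n = 22: (1.6416 − 1.2982)/0.6144 = 0.559, power 71.2%.
- n = 25: (1.7500 − 1.2982)/0.6144 = 0.735, power 76.9%.

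At one-sided 5% and n = 22 the same formula gives 81.6%, which is where the 80% claim comes from.

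**Step 3: power of the 8.3 rule itself.** Sum the binomial probabilities (0.85 and 0.50) over every pair of outcomes for which ln(OR) − 1.96 × SE > 0, where SE = √(1/a + 1/b + 1/c + 1/d) and 0.5 is added to all cells if any is zero. Because 8.3 names no interval method, other choices are shown as well.

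| Rule | 22 per group | 25 per group | 28 per group |
|---|---|---|---|
| Wald odds-ratio 95% interval | 68.5% | 77.4% | 81.3% |
| Wald, zero-cell tables counted as non-significant | 65.8% | 75.7% | 80.2% |
| Pearson | 71.6% | 79.0% | 83.1% |
| Likelihood ratio | 74.7% | 79.0% | 83.6% |
| Fisher/exact | 60.8% | 67.6% | 75.2% |

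The Wald rule gives 71.8% at 23 and 74.8% at 24. It first reaches 80% at 28 (79.6% at 27); the pooled formula first reaches it at 27. With both true rates at 50%, the Wald rule declares improvement 2.44% of the time at 22 and 2.25% at 25, which confirms that it runs at about one-sided 2.5%.

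**Step 4: which count applies.** With the plan's own 10% loss, 25 × 0.9 = 22.5, so about 22–23 per group are evaluable. The figure at 25 assumes no loss.

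**Step 5: what 80% power would detect.** Against 50% in control, the detectable NMES rate is about 88–89% with 22 per group (88.1% by formula, 88.9% by enumeration) and about 86% with 25.

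**The case against.** The figure of 22 is not a slip in arithmetic. It is correct for a one-sided 5% test, and the rule in 8.3 is worded in one direction, so a one-sided plan is a natural guess. That stands, and it makes this an inconsistency between two sections rather than a miscalculation. But 8.2 does not say one-sided, and the interval in 8.3 is a 95% one.

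The power figures also depend on an interval method the plan leaves open: 60.8% to 74.7% at 22 and 67.6% to 79.0% at 25 across the methods tabulated. This too stands, and the method should be named. It does not rescue the claim, because none of them reaches 80% at 22 to 25.

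At 25 per group the gap is small (79.0% by Pearson), and the unpooled two-sided formula gives 81.3% there. That formula approximates a risk-difference test rather than the odds-ratio rule, it gives only 76.2% at 22, and 8.2 makes its claim at 22.

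Finally, this is the second phase of three with a feasibility aim (section 1.1), and the 8.3 rule does not inflate false positives or bias the estimate. Modest power may well be acceptable in that setting. A power statement that does not match the analysis is a separate matter and still needs correcting.

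**Conclusion.** The statement in 8.2 is wrong as written when read with 8.3. Under the 95% interval rule, power for 85% against 50% is about 69–71% with 22 evaluable per group and about 77% with 25. The chance of missing the assumed effect is then about 30% or 23%, not 20%. About 27–28 evaluable per group are needed for 80%.

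This assumes that the 95% interval is the usual two-ended one, that the rates in 8.2 are true, and that the interval is Wald or close to it; an exact interval would do worse. That 8.2 used a one-sided test is inferred from the reproduction of 22, since the text is silent. The two statements in 3.3.2 on replacement leave the evaluable number unsettled, but the conclusion holds for every count from 22 to 25.

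**What to change.** Keep the rule in 8.3, call the interval two-sided, and name its method, including how zero cells are handled. Restate 8.2 to match, for example:

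> For the two-sided 95% confidence interval for the odds ratio, power to detect 85% against 50% is about 69–71% with 22 evaluable participants per group and about 77% with 25. With 22 per group, the NMES rate detectable with 80% power is about 88–89%.

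These figures suit a Wald interval and should be recomputed if another method is chosen. Section 3.3.2 should also say whether withdrawals are replaced, so that the evaluable number is clear. The cost is wording only: no extra participants, but a less favourable stated power.

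If 80% power is to be kept under this rule, the trial must be larger: 27/0.9 = 30 enrolled per group (60 in all) by the pooled formula, or 28/0.9 = 31.1, so 32 per group (64 in all), by enumeration of the Wald interval.

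If a one-sided 5% test was intended, both sections should say so and justify it before any data are analysed, using the lower end of a 90% interval. With the Wald interval, power is then 80.8% at 22 and 86.5% at 25. The false-positive rate at 50% in both groups is 4.8% at 22 but 5.95% at 25, and the text should disclose this. The choice cannot wait for the data: 17/22 against 11/22 gives an odds ratio of 3.4 with a lower limit of 0.93 on the 95% interval but 1.14 on the 90% interval.

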8.3 Statistical methods

Describe the statistical methods (or non-statistical methods of analysis) that will be employed.

We will recruit 25 participants to participate in the NMES intervention and 25 for standard rehabilitation (control). Summary statistics for variables of interest including recruitment, retention, adherence, and reported pain will be calculated. To test the difference between groups (NMES and control), we will quantify the odds ratio and the 95% confidence interval of performing a single heel-rise test. If the bottom end of the confidence interval is higher than 1.0, the improvement will be significant. Chi-square goodness of fit will be used to study the associations between groups and covariates such as gender, activity, and age. Cochran-Mantel-Haenszel test will be used to evaluate the consistency of such associations.

Protocol deviations, such as missing visits, or lost to follow up (within the 10% already considered in the power analysis) will have a negligible effect on the statistical analysis since the proposed analysis can have unbalanced groups. The planned interim safety analyses will quantify the odds ratio between adverse events in the intervention group and standard of care. If the bottom end of the confidence interval is higher than 1.0, the incidence of AEs in the intervention group will be significant higher than that of standard care.

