7.1 Study Design

Describe and explain the study design.

This is a randomized clinical trial with two groups: control and stimulation. Participants will be randomly assigned to a NMES (active) treatment or control group in a 1:1 ratio. No stratification factors will be considered in the randomization process based on covariates such as gender, activity, and age. In the stimulation group, subjects will receive standard rehabilitation and NMES will be applied to calf muscles 6 weeks after repair surgery. The pad placement and stimulation parameters will be updated in a weekly basis for the stimulation group. The control group will follow standard rehabilitation and will not receive NMES. For both groups, ultrasound evaluation will be performed at week 6 and 12 weeks after surgery. The primary outcome (heel-rise) will be measured at week 12 after repair. Other outcomes (activity level, pain) will be measured daily for the first 6 weeks after repair.

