Self-reported diary and outcomes: To evaluate frequency of loading, from the day after surgery, participants will complete a diary (paper or electronic survey via REDCAP) on estimated daily weightbearing load, number of steps/days with a pedometer placed at the hip, and pain on a visual analogue scale (VAS). Although standard of care prescribes no weight-bearing during the first two weeks after repair, patients are active during that period of time. The level of activity (steps), even though does not involve the use of the injured limb, can help explain potential differences in self-reported outcomes, especially kinesiophobia scores. These measurements are not part of the standard of care. Self-reported outcomes will be also collected at weeks 6 and 12: the Achilles tendon Total Rupture Score (ATRS) [56], the Physical Activity Scale (PAS) [57], the Foot and Ankle Outcome Score (FAOS) Quality of Life subscale [58], and the Tampa Scale of Kinesiophobia (TSK) [59], [60]. Patient reported outcomes (ATRS, PAS and FAOS) are part of the standard of care for Achilles tendon rupture.

Single heel-rise tests: The ability of performing a single heel-rise will be evaluated at week 12. The participants will stand on a flat box with the ankle in neutral position and will be asked to perform a single heel-rise. The participants will be classified as being able to perform a one-legged heel-rise if they were able to lift the heel at least 2 cm once while keeping the knee straight [60]. MuscleLab® (Ergotest Technology, Oslo, Norway) measurement system will be used for the evaluations as previously described in our previous study [29]. This will be performed in the physical therapy clinic at [name]. This test is not part of the standard of care for Achilles tendon rupture.

Table 3. Study Procedures for Stimulation and control groups

Week	Procedure
1	Consenting, Randomization, Distribution of diary and activity monitor, Demonstration of NMES (stimulation group only), (in-person visit)
2, 4	Adjustment of NMES (stimulation group only), collection of steps, and diary data. (Visit 2 can be done virtually with a video call, visit four should be done in person.)
6	Ultrasound Imaging, Questionnaires (ATRS, PAS, FAOS, TSK), collection of steps and diary data, Discontinue use of NMES (stimulation group only). (In-person visit)
12	Ultrasound Imaging, Heel-rise test, Questionnaires (ATRS, PAS, FAOS, TSK) (In person visit)

7.2.1 Visit 1 (Week 1).

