Provide a description of what procedures will be performed on visit 1 or day 1 or pre-test in order of how these will be done. If your study only involves one session or visit, use this section only and indicate 7.2.2 as not applicable.

This visit will be scheduled in first week after the surgery. The research team or clinician of the research team will demonstrate the NMES procedure to the participants. The research team will verify that the procedure is applied properly and follows with the protocol. An explanation of the information needed for the diary will also be provided. Participants will take the NMES device (for the treatment group) and the diary home and perform the procedure by themselves. Randomization will be communicated to the patient at this visit. Participants are provided the pedometer at this visit, and instructions on how to use it. The study team will not collect AEs at this visit. The total duration of this visit is estimated to be 45 minutes.

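### Section 8.3 names the wrong tests for two supporting covariate analyses: goodness of fit for association between arm and covariate, and Cochran-Mantel-Haenszel for consistency; the primary odds ratio is unaffected

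*Combined protocol and SAP*

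**What the plan says.** Section 8.3 gives the primary analysis first: the odds ratio for a single heel-rise with its 95% confidence interval, counted as significant if the lower limit exceeds 1.0. Two supporting analyses follow. The first: "Chi-square goodness of fit will be used to study the associations between groups and covariates such as gender, activity, and age". The second: "Cochran-Mantel-Haenszel test will be used to evaluate the consistency of such associations". Nothing else in the document describes these analyses. It names no test of independence, no test of homogeneity, no arm-by-covariate interaction and no age categories.

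Section 8.3 does not say which activity measure is the covariate. Elsewhere the word is attached to data collected after surgery:

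- Section 7.1: "Other outcomes (activity level, pain) will be measured daily for the first 6 weeks after repair".
- Section 7.2, on the diary, equates activity with pedometer steps: "The level of activity (steps), even though does not involve the use of the injured limb".
- Section 7.2 schedules the Physical Activity Scale (PAS) among the questionnaires: "Self-reported outcomes will be also collected at weeks 6 and 12".
- Section 1.3 lists both steps and PAS as secondary endpoints.

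Section 7.1 also names gender, activity and age as covariates on which randomisation will not be stratified.

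**The concern.** A goodness-of-fit test compares one observed distribution with a specified one. It does not ask whether two variables are associated, and the plan gives no reference distribution. If the reference is equal cells, the test rejects whenever the covariate itself is unevenly split, even when the arms match exactly. The report would then show an imbalance that does not exist.

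CMH tests whether a common odds ratio across strata equals 1. If it is meant to show that stimulation works alike in men and women or across ages, it tends to answer the wrong way round: usually significant when the effect is uniform, and often not significant when the effects oppose each other. A significant CMH result would not show consistency, and a non-significant one would not show inconsistency.

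Both tests also need categories, and none are given for age. Because activity is undefined, two analysts could use different variables.

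**Working it through.** The plan states no figure for these analyses, so there is none to reproduce. Inputs from the plan: heel-rise rates of 50% (control) and 85% (NMES) from section 8.2, and 25 per arm from section 8.3. Sex splits and stratum sizes are assumptions. All tests are at the two-sided 5% level.

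**1. Goodness of fit against independence, one table.** Assume 20 men and 5 women in each arm. Against equal cells the expected count is 50/4 = 12.5. Each cell differs from it by 7.5, so chi-square = 4 × 7.5²/12.5 = 18.0 on 3 df, p=0.0004. Under independence the expected counts are 20, 5, 20 and 5, so chi-square = 0, p=1.0.

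**2. How often each test rejects when arm and sex are unrelated** (exact enumeration, 25 per arm):

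| True % men | Equal-cells goodness of fit | Independence |
|---|---|---|
| 50 | 1.7% | 6.5% |
| 60 | 11.9% | 6.0% |
| 70 | 59.6% | 5.4% |
| 80 | 97.2% | 5.5% |

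**3. CMH against Breslow-Day, one table.** Heel-rise yes/no; 25 per arm in total.

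- Stratum 1: NMES 11/2, control 4/8. OR = (11×8)/(2×4) = 11.0. Expected NMES successes 13×15/25 = 7.8; variance 13×12×15×10/(25²×24) = 1.56.
- Stratum 2: NMES 4/8, control 10/3. OR = (4×3)/(8×10) = 0.15. Expected 12×14/25 = 6.72; variance 12×13×14×11/(25²×24) = 1.6016.
- CMH without continuity correction = [(11−7.8)+(4−6.72)]²/(1.56+1.6016) = 0.48²/3.1616 = 0.073, p=0.79.
- Pooled OR = (88/25+12/25)/(8/25+80/25) = 100/88 = 1.14.
- Breslow-Day p=0.0007.

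The strata point in opposite directions, and CMH reports nothing.

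**4. Rejection rates with the section 8.2 rates** (exact enumeration, same stratum sizes in both arms, CMH uncorrected). Uniform means 85% v 50% in both strata; reversal means 85% v 50% in one and 50% v 85% in the other. Breslow-Day ranges span the raw test and the test with 0.5 added in strata that have a zero cell.

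| Strata per arm | CMH, uniform | CMH, reversal | Breslow-Day, reversal |
|---|---|---|---|
| 13 and 12 | 78% | 4% | 79–80% |
| 18 and 7 | – | 20% | 71–72% |
| 20 and 5 | 78% | 35% | 61–64% |

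With continuity correction the uniform rate at 13 and 12 falls to 67%. With the section 8.2 minimum of 22 per arm (11 and 11 assumed) it is 72% uncorrected and 58% corrected.

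**5. What a homogeneity test can deliver.** If only one stratum benefits, Breslow-Day rejects in 29–31% of trials at 13 and 12. At 20 and 5 it rejects in 24–25% if the larger stratum benefits and 12–19% if the smaller does.

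**6. Timing of the activity measures.** The diary text says "from the day after surgery, participants will complete a diary". Table 3, however, places "Consenting, Randomization, Distribution of diary and activity monitor" together in week 1, and the Visit 1 description says "Participants are provided the pedometer at this visit, and instructions on how to use it". PAS comes at weeks 6 and 12. As scheduled, then, neither steps nor PAS is a pre-allocation measure. The separate screening questionnaire mentioned in section 4.2.4 may hold a baseline activity item; this cannot be checked here.

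**The case against.** Four objections carry weight.

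**The goodness-of-fit figures rest on a null the plan never states.** Pearson's chi-square with expected counts taken under independence is the correct test, and the wording is most likely loose naming for it. That stands: the 60% and 97% rejection rates describe a literal reading, not a predicted analysis. The named test is still wrong.

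**The CMH figures depend on one reading.** Grammatically, the associations in the second sentence are those between arm and covariate; heel-rise is not mentioned there. Consistency may also mean that an association persists after stratification, which CMH does address. That stands too, so the rates in step 4 are conditional. Under full reversal, CMH is rarely significant only when the strata are near equal. The text still does not say which meaning applies.

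**The activity point is easily overstated.** A reader might infer that the trial will stratify on steps or PAS recorded after randomisation and so condition on an outcome. The documents do not support this. Section 8.3 never says that either will be a baseline covariate or stratifier, and section 7.1 lists activity beside gender and age as possible randomisation factors, which points to something known before allocation. What remains is that the measure is not named.

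**The consequence is small.** No decision rule uses these tests, and a homogeneity test at this size has low power. Both are correct, and they limit the severity.

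**Conclusion.** The point holds as a low-severity correction. As written, section 8.3 gives goodness of fit a job that belongs to a test of independence, and gives CMH a job that, on one plausible reading, belongs to a test of homogeneity. The first is probably a slip of naming; its illustrated size (p=0.0004 against p=1.0) assumes an equal-cells null and a 20/5 sex split. The second matters only if consistency refers to the heel-rise effect. Under the section 8.2 rates and assumed strata of 13 and 12 per arm, CMH is then significant in 78% of trials with a uniform effect (67% with continuity correction) and 4% with full reversal, rising to 20% and 35% as the strata become unequal.

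A reader might infer that the trial's main conclusion is at risk. It is not: the unadjusted odds ratio and its confidence-interval rule do not depend on either test. The missing age cuts and the undefined activity measure are matters of clarification only.

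**What to change.** In section 8.3:

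1. Replace goodness of fit with a chi-square test of independence, or Fisher's exact test where cells are small.
2. State what consistency refers to. If it is the heel-rise effect across sex or age, assess it with Breslow-Day or an arm-by-covariate interaction, with age continuous or in prespecified categories. Report stratum odds ratios with 95% confidence intervals and label the analysis exploratory.
3. Keep CMH for a stratum-adjusted common odds ratio.
4. As a minor clarification, name the activity measure. If it serves as a baseline covariate, use one recorded before allocation.

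The primary analysis stays as it is. The cost is a few sentences in 8.3, with no change to sample size or visits, provided that any pre-allocation activity measure is already collected at screening; if not, one item would have to be added there. The drawback is low power: about 12–31% if only one stratum benefits, depending on stratum sizes. A non-significant homogeneity result would therefore not show that the effect is alike, and the report should say so.
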